### Revision Chronology

GlaxoSmithKline Document Number	Date	Version
2015N227551_00	2016-JUN-13	Original
2015N227551_01	2017-MAY-24	Amendment No. 1

• Updates to some T&E windows (pregnancy tests, V1 for FRP and minor salivary gland biopsy)

• Flexibility to allow follow up for pSS subjects by telephone.

• Updates to blood tests as per file notes issued during study.

• Typographical error in Section 9.2 changed from “within approximately 0.62 of the point estimate” to “within approximately 0.64 of the point estimate”.

• Minor formatting changes

		

## 1. PROTOCOL SYNOPSIS FOR STUDY 203818

### Rationale

This is a pilot imaging study designed to assess whether molecular imaging with  $^{18}\text{F}$ -fluorodeoxyglucose (FDG) positron emission tomography (PET)/computed tomography (CT),  $^{11}\text{C}$ -Methionine (MET) PET/CT and salivary gland magnetic resonance imaging (MRI) have the potential to characterize and quantify disease manifestations in primary Sjögren's syndrome (pSS) subjects. This will be achieved by assessing the associations and consistency between the imaging techniques studied, clinical assessments (salivary and tear flow and clinical scores), laboratory biomarkers and histological findings on minor salivary gland biopsy. It is hoped that the methodologies may help with the selection of subjects, and/or assessments of treatment response in future clinical studies. For example, subjects with on-going inflammation and a degree of gland function might be more suitable for anti-inflammatory therapies.

### Objective(s)/Endpoint(s)

Objectives	Endpoints
Primary	

 
To investigate the use of <math>^{18}\text{F}</math>-FDG PET/CT in assessing increased glucose uptake as a biomarker of inflammation in pSS subjects.
 
	
 
Semi-quantitative parameters of uptake in selected body areas, including salivary glands for <math>^{18}\text{F}</math>-FDG:               
 
Standardised uptake value (SUV)
 
Tissue-to-reference ratio
 
Total inflammatory volume (TIV) where anatomically relevant.
 
 
 

 
To investigate the use of <math>^{11}\text{C}</math>-Methionine (MET) PET/CT in assessing salivary glandular function in pSS subjects and healthy volunteers.
 
	
 
Semi-quantitative parameters of uptake in selected areas, including salivary glands for <math>^{11}\text{C}</math>-MET:               
 
SUV
 
Tissue-to-reference ratio
 
TIV where anatomically relevant.
 
 
 

 
To investigate the use of multi-parametric MRI in assessing salivary gland inflammation, function and structure in pSS subjects and healthy volunteers.
 
	
 
Quantitative parameters of uptake derived from multi-parametric MRI in the salivary glands including: exchange rate (<math>K_{\text{trans}}</math>), apparent diffusion coefficient (ADC), pure diffusion coefficient (D) and microvascular volume fraction (f) as data permits.
 

Objectives	Endpoints
Secondary	

 
To characterize the pharmacokinetics of <math>^{11}\text{C}</math>-MET PET tracer in vivo to allow static imaging parameters to be verified.
 
	
 
Generation of quantitative outcome parameters (rate of <math>^{11}\text{C}</math>-MET accumulation, as data permits) using a full quantitative analysis of dynamic PET scans.
 
Comparison of static and dynamic imaging metrics in <math>^{11}\text{C}</math>-MET.
 

Exploratory	

 
To explore the use of novel multi-parametric MRI in assessing salivary gland inflammation, function and structure in pSS subjects and healthy volunteers.
 
	
 
Quantitative parameters of uptake derived from multi-parametric MRI in the salivary glands including: initial rate of enhancement (IRE), maximal signal intensity enhancement (ME), lipid content, T1 relaxation, and volume, as data permits.
 

 
To explore the associations of the salivary gland imaging parameters with clinical and histological parameters of salivary glands.
 
	
 
Association between <math>^{18}\text{F}</math>-FDG PET/CT (pSS subjects only), <math>^{11}\text{C}</math>-MET PET/CT and MRI parameters (healthy volunteers and pSS subjects) in the region of the salivary glands with each other and with clinical measures including: 
 
Basal and stimulated salivary flow
 
Histological scores from minor salivary gland biopsies including but not limited to lymphocyte count and focus score (pSS subjects)
 
Laboratory biomarkers of disease activity (including metabolomic and/or proteomic profiles where applicable)
 
European League Against Rheumatism (EULAR) Sjögren's Syndrome Disease Activity Index (ESSDAI) and EULAR Sjögren's Syndrome Patient Reported Index (ESSPRI), in particular subcomponents relevant to salivary gland function (pSS subjects).
 
 
 

Objectives	Endpoints

 
To explore the extent of non-salivary gland (systemic) abnormalities detected on F-FDG PET/CT and C-MET PET/CT, and the association of these abnormalities with clinical scores/relevant sub-scores and laboratory biomarkers in pSS subjects.
 
	
 
Semi-quantitative parameters in selected areas systemically for F-FDG and C-MET (including but not limited to lymph nodes, thyroid, lacrimal glands, lungs and pancreas) and the associations of these parameters with: 
 
Laboratory biomarkers of disease activity (including metabolomic and/or proteomic profiles where applicable)
 
Lacrimal gland function as measured by Schirmer's test
 
ESSDAI and ESSPRI and organ-specific subcomponents relating to the area imaged, where available.
 
 
 

 
To compare the metabolomic profiles of pSS subjects and healthy volunteers, to assess the intra-individual variability of the metabolome over time, and the ability of samples from different bodily sites to discriminate pSS subjects from healthy volunteers.
 
	
 
Compare the metabolome/proteome of pSS subjects with healthy volunteers.
 
Assess the variability in the metabolome and/or proteomic profile of individual subjects taken at 2 separate time points (Baseline and Visit 2).
 
Compare the metabolome and/or proteomic profile from different body fluids/sites, and their utility in distinguishing pSS subjects from healthy volunteers.
 
Samples collected will be saliva, tears and plasma.
 

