## Treatment Arms and Duration

### Subject Participation Flow

Both groups will undergo a Screening/Baseline visit where they will have measurement of basal and stimulated, salivary flow rate (including saliva collection), Schirmer's test and blood samples for biomarkers. The pSS subjects will also have additional clinical scores and patient reported assessments.

Subjects who have completed the screening/baseline will return for an imaging visit (Visit 1). The imaging visit should occur within 6 weeks (42 days) after the screening visit. The following imaging procedures will be performed:

- Group A (healthy volunteers) will undergo an MRI of the salivary glands and C-MET PET/CT (dynamic scan of the salivary glands followed by head to hip static scan).

- Group B (pSS subjects) will undergo an MRI of the salivary glands,  $^{11}\text{C}$ -MET PET/CT (as for Group A) and  $^{18}\text{F}$ -FDG PET/CT (static scan head to hip).

Visit 2 will occur within 3 weeks after Visit 1. Visit 2 will involve measurement of basal and stimulated (chewing paraffin) salivary flow rate (including saliva collection), Schirmer's test (including tear collection), blood samples for biomarkers (metabolomics/proteomics). In addition a minor salivary gland biopsy will be performed on the pSS subjects (Group B). If it is not possible, for logistical or other reasons to schedule the minor salivary gland biopsy within 3 weeks of Visit 1, then this part of Visit 2 may be performed up to 6 weeks after Visit 1, with the prior agreement of the medical monitor.

There will be a Follow up visit within 2 weeks of Visit 2. This may be conducted by telephone for the healthy volunteers (Group A). The pSS subjects (Group B) may have their Follow up visit conducted in person, or by telephone if the Investigator considers it clinically appropriate. Adverse events (AE) will be reviewed at this visit for all of the subjects (Group A and Group B).

Visit 1 and Visit 2 may be split over more than one day.

The total duration of participation in the study will be a maximum of 11 weeks (up to 14 weeks only if it is necessary to delay the minor salivary gland biopsy), although the visits should be completed sooner if feasible.

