#### CONCOMITANT MEDICATIONS

14. Group A: healthy volunteers. Subject is unable to refrain from taking prescription or non-prescription drugs (including vitamins and dietary or herbal supplements), within 7 days prior to Visit 1 until completion of Visit 2, unless in the opinion of the investigator and Sponsor the medication will not interfere with the study.
15. Group B- pSS subjects taking immunomodulatory treatment at screening are excluded unless they have been on stable doses of these medicines for 6 weeks prior to Screening/Baseline and are expected to remain on stable doses of these medications until the Follow up visit. This would include drugs such as glucocorticoids, immunosuppressive agents (for example hydroxychloroquine, azathioprine, methotrexate, mycophenolate mofetil, and biologic therapies). Permitted medications are listed in Section 6.8. If in doubt please discuss with the Medical Monitor.
16. Group B: pSS subjects. Receiving treatment with anti-coagulant medications, including but not limited to warfarin, heparin, thrombin inhibitors, and Factor Xa inhibitors, and aspirin, unless the subjects is able to discontinue these medications one week prior to minor salivary gland biopsy, or according to local guidelines. The treatment may be restarted 3 days after the biopsy, or according to local guidelines.

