## **6.8. Concomitant Medications and Non-Drug Therapies**

### **6.8.1. Permitted Drug Therapies (Group B: Primary Sjögren's Syndrome Subjects)**

- Stable doses of potentially immunomodulatory treatments are permitted (stable from 6 weeks prior to screening until follow up). This includes potentially disease modifying drugs such as glucocorticoids, immunosuppressive agents (*eg* hydroxychloroquine, azathioprine, methotrexate, mycophenolate mofetil, and biologic therapies). The investigator should discuss drug therapies with the Medical Monitor if they have any safety concerns or are unsure about the potential impact on the scientific validity of the study data.
- Topical symptomatic therapies (such as [a] non-medicated ocular topical drops: saline or glucane; [b] non-pharmacologic oral topical agents: chewing gum, saliva substitutes) are permitted. Subjects will be required to withhold dosing with these agents in the 2 hours prior to collection of saliva and tear samples at Screening/Baseline visit and Visit 2.
- Oral muscarinic agonists (such as pilocarpine and cevimeline) are permitted. Subjects will be required to withhold dosing with these agents in the 12 hours prior to the Screening/Baseline visit and Visit 2.
- Anticholinergic agents, such as tricyclic antidepressants, bupropion, antihistamines, phenothiazines, antiparkinsonian drugs, anti-asthmatic medications, or gastrointestinal medications that cause xerostomia in more than 10% of patients are permitted provided that a subject is on a stable regimen for at least 4 weeks prior to Screening/Baseline visit until follow up has been completed.

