### **6.8.2. Prohibited Medications and Non-Drug Therapies**

#### **Group A: Healthy Volunteers**

- Healthy volunteers are to refrain from taking prescription or non-prescription drugs (including vitamins and dietary or herbal supplements), within 7 days prior to Visit 1 until after Visit 2, unless in the opinion of the investigator and Sponsor the medication will not interfere with the study.

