The histological scores (see Section 11.3.5) and the various disease indices (see Section 11.3.4) – ESSDAI, ESSPRI, Patient and Physician global assessment of disease activity, oral and ocular dryness scales will be descriptively summarized and listed for pSS group only.

Descriptive statistics will be calculated for the exploratory multiparametric MRI quantitative derived parameters listed in Table 7 (as data permits) and presented in tables. All parameters will be listed by group (and ROI, as data permits). Mean (\pm SE bars) will be plotted for each parameter by ROI (if appropriate with panel for each side).

Correlation between ^{18}F -FDG PET/CT (pSS subjects only), ^{11}C -MET PET/CT and MRI parameters (HV and pSS subjects) in the region of the salivary glands (parotid gland) will be explored using scatter plots. Plots will be in panel for each side (most vs least uptake) of the region scanned. The parameters will include, SUV_{peak} for PET/CT and K_{trans} , D and f for multiparametric MRI.

Furthermore, correlation between the imaging parameters mentioned above and

- histological scores (mean and maximum lymphoid organisation score and volume fraction) from the minor salivary gland biopsy
- Salivary flow rate – mean (from baseline and visit 2) stimulated and basal salivary flow rate, and mean difference (stimulated – basal)
- Measures of Disease Activity – ESSDAI and ESSPRI scores
- Lab biomarkers of disease activity – C3 and C4 levels
- Schirmer's test – length of paper wetted by eyes (panel for each side; least and most) and time to completely wet the strip (panel for each side; least and most).

may be explored using scatter plots (panel for each side) and statistical analysis summarised in tables. In addition, SUV_{peak} from the ^{11}C -MET PET/CT will be correlated with the ratio of IgG/IgA using scatter plots and summary tables of the correlation. See below for summary of correlations:

CONFIDENTIAL

203818

Method		11C-MET PET/CT	18F-FDG PET/CT	Multiparametric MRI
	Parameter(s)/Endpoint	SUVpeak	SUVpeak	(median) Ktrans, (median) D, (median) ADC, (median) f, (median) IRE, (median) ME, (mean) Lipid Content, (median) D* (pseudo diffusion), (mean) gland volume
11C-MET PET/CT	SUVpeak		Yes	
18F-FDG PET/CT	SUVpeak	Yes		
Multiparametric MRI	(mean) lipid content	Yes	Yes	Yes ¹
Histological scores	Max lymphocyte focus score	Yes	Yes	Yes
	Mean lymphocyte focus score			
	Max Lymphoid organisation grading			
	Mean Lymphoid organisation grading			

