11.3.7. Salivary Flow Rate

Salivary Flow Rate

Salivary flow rate is measured at basal and stimulated state at screening/baseline and at follow-up.

Mean of baseline and follow-up visit will be calculated separately for stimulated and basal salivary flow rate. The mean will be calculated as:

- Mean Stimulated/Basal salivary flow = $(\text{Stimulated/Basal salivary flow at baseline} + \text{Stimulated/Basal salivary flow at follow-up}) \div 2$.

If value is missing at one time point (e.g. baseline), then the rate from the other time (follow-up) will be used for the mean.

The difference of the stimulate and basal salivary flow rate will be calculated for each time point:

- Screening/baseline difference = Stimulated salivary flow rate at baseline - Basal salivary flow rate at baseline
- Follow-up difference = Stimulated salivary flow rate at follow-up – Basal salivary flow rate at follow-up.

If one of the rate (stimulated or basal) is missing at one time point (e.g. baseline), then the rate

from the other time (follow-up) will be used to calculate the difference. If the measure of the rate is missing at both time points, then difference will be set to missing.

The mean of difference (stimulated-basal) will be derived as follows:

- Mean difference (stimulated – basal) salivary flow = (Screening/baseline difference + Follow-up difference) ÷ 2

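### Healthy volunteers' Baseline samples and salivary flow can predate their drug-free window, so Baseline-to-Visit 2 variability and two-visit mean flow may carry an unidentified drug-stopping effect

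*Protocol*

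**What the plan says.** **Use of the two visits.** The protocol synopsis lists as an endpoint: "Assess the variability in the metabolome and/or proteomic profile of individual subjects taken at 2 separate time points (Baseline and Visit 2"). Protocol section 3 and SAP 2.2 repeat it. For flow, SAP 9.1.1 correlates imaging with the "mean (from baseline and visit 2) stimulated and basal salivary flow rate", and SAP 11.3.7 gives the rule: "Mean of baseline and follow-up visit will be calculated separately for stimulated and basal salivary flow rate". SAP 11.3.7 calls the second reading follow-up, but Protocol Table 3 places it at Visit 2 and schedules none at Follow up. If one reading is missing, SAP 11.3.7 uses the reading from the other visit.

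**Timing.** Protocol synopsis: "The imaging visit should occur within 6 weeks (42 days) after the screening visit" and "Visit 2 will occur within 3 weeks after Visit 1". Saliva, tears, plasma and flow are taken at Screening/Baseline (Protocol Table 2) and again at Visit 2 (Table 3). The scans are at Visit 1.

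**Healthy volunteers.** Exclusion 14 requires them to be able to refrain from drugs, vitamins and supplements "within 7 days prior to Visit 1 until completion of Visit 2". Section 6.8.2 sets the same window with an exception: "within 7 days prior to Visit 1 until after Visit 2, unless in the opinion of the investigator and Sponsor" the product is considered harmless to the study.

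**pSS subjects.** Section 6.8.1 allows immunomodulators at steady doses, "stable from 6 weeks prior to screening until follow up". It asks for a steady regimen of drying (anticholinergic) agents from 4 weeks before Baseline. Both rules are listed for Group B only. Exclusion 16 and section 6.8.2 also provide for anticoagulants and aspirin to be stopped before the biopsy.

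**The concern.** The variability endpoint and the flow average both treat Baseline and Visit 2 as two readings of the same subject in the same state. For a healthy volunteer that need not be so. The medicine restriction usually opens after Baseline, and the rules that Protocol section 6.7 sets for both sampling visits do not fill the gap. They cover fasting, alcohol, oral products and smoking, eye products and lenses, and a 12-hour hold on oral muscarinic agonists. They do not cover other systemic drugs.

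Any volunteer who stops a product between Baseline and Visit 2 then adds the effect of stopping to the estimate of natural variation over time. The same volunteer's averaged flow mixes two drug states and is set against a scan taken in only one of them. Products judged harmless may continue, so those that must stop are the ones not cleared. The protocol's stability rule for drying agents in pSS subjects shows that its authors saw medication as relevant to flow.

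At stake is how the volunteers' within-subject variability and averaged flow are read. The SAP defines no medication-change indicator, and subject group is the only term in its models (SAP 11.7).

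**Working it through.** **Plan's own figure.** The documents give no figure for within-subject variability or for volunteers' medicine use. Their only precision figures are in Protocol Table 5, and these reproduce: for SD 1 and N = 12, 2.201 × 1/√12 = 0.635, printed as 0.64. Those are precisions of a mean across subjects and do not enter this point.

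**Dates.**
- Longest time from Baseline to the opening of the window: 42 − 7 = 35 days without restriction.
- Longest time from Baseline to Visit 2: 42 + 21 = 63 days.
- Baseline lies inside the window only if Visit 1 follows within 7 days.

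**Model.** Work in units of the true within-subject SD. A share p of volunteers has a shift of r at Baseline and none at Visit 2. Let d be the difference between the two visits.
- Within-subject variance, E[d²]/2, is multiplied by 1 + p·r²/2.
- The group mean of the two-visit average shifts by p·r/2. Each affected subject shifts by r/2, or by the full r if Visit 2 is missing and SAP 11.3.7 uses Baseline alone.

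**Inputs.** Neither p nor r is in the documents. The ranges 0.10 to 0.50 and 0.5 to 2 are assumptions.

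| p | r | Variance factor | SD factor | Shift in mean averaged flow (SD) |
|---|---|---|---|---|
| 0.10 | 0.5 | 1 + 0.10×0.25/2 = 1.01 | 1.006 | 0.025 |
| 0.25 | 1 | 1 + 0.25×1/2 = 1.125 | 1.06 | 0.125 |
| 0.50 | 2 | 1 + 0.50×4/2 = 2.0 | 1.41 | 0.5 |

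A simulation at p = 0.25, r = 1 gave 1.125 and 0.126, against 1.125 and 0.125 from the formulas. If the variability estimate is centred on the group's mean change, the variance factor is 1 + p(1 − p)·r²/2, and the SD factors fall to 1.006, 1.05 and 1.22. At p = 0 there is no inflation and no shift.

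**Flow-imaging correlations.** Affected subjects add p(1 − p)·r²/4 to the variance of averaged flow: 0.25×0.75×1/4 = 0.047 in the middle row and 0.5×0.5×4/4 = 0.25 in the last. Ordinary error in a two-visit mean already contributes 1/2 = 0.5, and real differences between subjects come on top. If medicine use is unrelated to the imaging value, the correlation is weakened only slightly. Visit 2 flow alone has error variance 1.0, so using it adds 0.5 of noise to remove at most 0.25 over this range. It therefore suits a sensitivity analysis, not a replacement.

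**The case against.** The strongest reply is that this is a conditional caveat on exploratory endpoints. Volunteers are healthy on medical evaluation, so few may take anything that matters. Medication is already reviewed at Screening, Visit 1 and Visit 2 and is reported in SAP Table 1.7 and Listing 9, so a careful reader could find the changers. Metabolomic and proteomic work is optional and, under SAP 9.1.1, may be reported separately and outside the main report. All of that stands and limits the weight of the point. It does not close the gap, because a listing does not keep a drug effect out of an estimate.

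A reader might also infer more than the documents support:

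- *That only the control group changes drug state.* pSS subjects who stop anticoagulants or aspirin for the biopsy, a Visit 2 procedure, can show the same pattern. A flag for volunteers alone would create an imbalance of its own.
- *That a comparison between the groups is biased.* No comparison of volunteer with pSS variability is planned, and none of flow. The SAP's group comparisons are of imaging parameters (7.1.2, 7.1.3, 9.1.2), and the volunteers' scans fall inside the drug-free window.
- *That SAP Table 5.6 reports a distorted two-visit mean.* SAP 9.1.1 describes absolute values, and the table's footnote defines the difference within a time point. Averaging is specified for the correlations.
- *That the inflation is known to be large.* With an assumed within-subject log SD of 0.20 and a 40% Baseline effect in a quarter of volunteers, the SD becomes √(0.04 + 0.25×0.511²/2) = 0.27, or 35% higher. That needs a shift of 0.511/0.20 = 2.6 within-subject SDs, beyond the range used here and without support in the documents. A drug also need not move every metabolite or protein.

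**Conclusion.** The timing gap is real, and no other provision closes it. Medication changes between Baseline and Visit 2 can enter the metabolome/proteome variability estimate and the averaged flow, and the plan neither identifies nor removes them. Neither size nor direction can be stated from the documents. Over the assumed ranges the effect runs from negligible (variance ×1.01, mean shift 0.025 SD) to material (variance ×2.0, mean shift 0.5 SD), and it is nil if nobody changes medication. Averaged flow is affected mainly in level; the effect on its correlations with imaging should be small. Primary imaging comparisons are unaffected. This is a worthwhile low-cost improvement, not a threat to the study's main conclusions.

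**What to change.** In SAP 9.1.1 and 11.3.7, and in any separate metabolomic/proteomic plan:

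1. From the existing concomitant-medication record, derive a flag for any subject in either group who stopped or started a drug or supplement between Baseline and Visit 2. Include pSS subjects who stop anticoagulants or aspirin for the biopsy. Query partial stop dates before deriving it: SAP 11.4.2.2 imputes them late, so a stopped medicine could look continued.
2. Report Baseline-to-Visit 2 metabolome/proteome variability with and without flagged subjects, and list flagged subjects separately.
3. Keep the two-visit mean for the planned flow-imaging correlations, and repeat Table 5.7 and Figures 5.1 to 5.3 with Visit 2 flow only as a sensitivity analysis.
4. Present Table 5.6 by visit, with no Baseline data deleted.
5. For flagged subjects, do not carry a flow value from one visit to the other under SAP 11.3.7. Otherwise a stimulated-minus-basal difference could combine two drug states.
6. Correct the follow-up label in SAP 11.3.7 to match the visit in Protocol Table 3.

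The cost is SAP wording and one derived variable, with no new data. The variability estimate without flagged subjects rests on fewer people, from a group of only 4 to 12 volunteers, and single-visit flow is noisier. No medication rule is proposed or altered; the sponsor should reconcile the different medication-stability windows that the protocol sets for the two groups.
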